NON-INTERVENTIONAL STUDY PROTOCOL

Study information

| | |
|---|--|
| Title | Post-Discharge Treatment Patterns and Outcomes in Patients with Venous Thromboembolism |
| Protocol number | B0661190 |
| Protocol version identifier | Version 1.0 |
| Date | 14 Feb 2023 |
| Active substance | B01AF02; Apixaban |
| Medicinal product | Eliquis |
| Research question and objectives | 
The purpose of this study is to evaluate the post-discharge treatment patterns including persistence, recurrent venous thromboembolism (VTE) and bleeding among hospitalized adult VTE patients treated with apixaban or warfarin.
 
The study objectives are as to:
 
1. Describe the proportion of patients with VTE treated with apixaban or warfarin in the hospital2. Understand the post-discharge treatment patterns (including persistence, switch, and discontinuation) among patients who started on apixaban or warfarin in the hospital 
The secondary objective is to:
 
3. Assess recurrent VTE, major bleeding, and clinically relevant non-major (CRNM) bleeding among patients who continue on apixaban or warfarin in the outpatient setting, while persistent on index therapy |

090177e19cc79c7f\Approved\Approved On: 03-Mar-2023 00:48 (GMT)

| Authors | |
|----------------|---|
| | PPD [REDACTED], MPH, PhD |
| | PPD [REDACTED] Pfizer, Inc. |
| | PPD [REDACTED] [REDACTED] |
| | PPD [REDACTED], MS |
| | PPD [REDACTED] [REDACTED] IQVIA, Inc. |
| | PPD [REDACTED] |
| | PPD [REDACTED], MHSA |
| | PPD [REDACTED] [REDACTED] IQVIA, Inc. |
| | PPD [REDACTED] [REDACTED] |
| | PPD [REDACTED], PhD, MBBS |
| | PPD [REDACTED] [REDACTED] IQVIA, Inc. |
| | PPD [REDACTED] |

This document contains confidential information belonging to Pfizer. Except as otherwise agreed to in writing, by accepting or reviewing this document, you agree to hold this information in confidence and not copy or disclose it to others (except where required by applicable law) or use it for unauthorized purposes. In the event of any actual or suspected breach of this obligation, Pfizer must be promptly notified.

090177e19cc79c7f\Approved\Approved On: 03-Mar-2023 00:48 (GMT)

2. LIST OF ABBREVIATIONS

| Abbreviation | Definition |
|---------------------|---|
| ACE | Angiotensin-converting enzyme |
| AIDS | Acquired Immune Deficiency Syndrome |
| ARB | Angiotensin Receptor Blockers |
| CCI | Charlson Comorbidity Index |
| CDM | Hospital Charge Data Master |
| COPD | Chronic Obstructive Pulmonary Disease |
| COVID-19 | Coronavirus Disease 2019 |
| CPT-4 | Current Procedural Terminology version 4 |
| CRF | Case Report Form |
| CRNM | Clinically-relevant non-major |
| DOAC | Direct Oral Anticoagulant |
| DCT | Data Collection Tools |
| DVT | Deep Vein Thrombosis |
| Dx | Professional Fee/ Medical Claims |
| ER | Emergency Room |
| HCPCS | Healthcare Common Procedure Coding System |
| HIPAA | Health Insurance Portability and Accountability Act |
| ICD-9-CM | International Classification of Diseases, ninth revision, clinical modification |
| ICD-10-CM | International Classification of Diseases, tenth revision, clinical modification |
| ID | Identifier |
| IEC | Independent Ethics Committee |

090177e19cc79c7f\Approved\Approved On: 03-Mar-2023 00:48 (GMT)

| | |
|-------|---|
| IQR | Interquartile Range |
| IRB | Institutional Review Board |
| LMWH | Low molecular weight heparin |
| LRx | Longitudinal prescription claims database |
| NSAID | Nonsteroidal anti-inflammatory drugs |
| OAC | Oral Anticoagulant |
| PAC | Parenteral Anticoagulant |
| PCP | Primary Care Provider |
| PE | Pulmonary Embolism |
| SAS | Statistical Analysis System |
| SD | Standard Deviation |
| SERM | Selective Estrogen Receptor Modulators |
| US | United States |
| VTE | Venous Thromboembolism |

090177e19cc79c7f\Approved\Approved On: 03-Mar-2023 00:48 (GMT)

4. ABSTRACT

Title

Post-Discharge Treatment Patterns and Outcomes in Patients with Venous Thromboembolism
Version: 1.0

Date: 14 Feb 2023

Primary author:

PPD

Pfizer, Inc.

Rationale and background

Venous thromboembolism (VTE), comprising deep vein thrombosis (DVT) and pulmonary embolism (PE), is a major health concern associated with significant mortality and morbidity. There are >330,000 hospital admissions for VTE every year in the United States (US).³ Historical data suggests that the rate of hospitalization for VTE increased from 7.0 to 8.4 per 1,000 discharges in the US.⁴

Management of VTE during an acute hospital encounter involves rapid anticoagulation. Current guidelines recommend continuing anticoagulation therapy post-discharge with warfarin, a vitamin K antagonist, or one of the newer direct oral anticoagulants (DOACs) which do not require Parental Anticoagulant (PAC) bridging therapy.⁵ Over the past decade, the use of DOACs, particularly apixaban, to treat VTE has increased dramatically.⁶

There are some gaps in real world evidence (RWE) regarding oral anticoagulant (OAC) use among patients hospitalized with VTE. First, there is a need for RWE regarding the proportion of patients treated with particular OACs during the VTE hospitalization. Second, there needs to be a better understanding of the OAC-related treatment patterns post-discharge following the VTE hospitalizations. There is evidence that a large proportion of patients treated in both inpatient and observational hospital settings do not fill an anticoagulant prescription post-discharge.⁷ Research shows that the choice of treatment regimen and/or setting could influence the likelihood of post-discharge continuation of OAC medication.⁷ This study will investigate the initial treatment patterns during VTE hospitalization and further investigate the treatment patterns post-discharge and factors associated with poor outcomes among these patients.

Research question and objectives

The purpose of this study is to evaluate the post-discharge treatment patterns including persistence and outcomes such as recurrent VTE and bleeding among hospitalized adults with VTE treated with apixaban or warfarin.

The study objectives are to:

1. Describe the proportion of patients with VTE treated with apixaban or warfarin in the hospital

2. Understand the post-discharge treatment patterns (including persistence, switch, and discontinuation) among patients who started on apixaban or warfarin in the hospital

The secondary objective is to:

3. Assess recurrent VTE, major bleeding, and clinically relevant non-major (CRNM) bleeding among patients who continue on apixaban or warfarin in the outpatient setting while persistent on index therapy

Study design

A retrospective database analysis will be conducted among patients hospitalized with a primary diagnosis of VTE. This study will utilize linked data from IQVIA's hospital charge master data (CDM), professional fee claims (Dx) and prescription claims (LRx) from 01 July 2017 through 31 December 2022 or the latest available data at the time of extraction (i.e., the *study period*), including 6-month pre-hospitalization period (starting the day before the admit date of hospitalization and a minimum 1-month post-hospitalization (starting a day after discharge date of hospitalization) period. The first apixaban or warfarin treatment during the index hospitalization will be flagged. Following discharge, patients who continue apixaban or warfarin, respectively, in the outpatient setting (with outpatient treatment claim occurring on or within 30-days following the discharge date) will be identified. The date of the first apixaban or warfarin claim will serve as the treatment index date. The baseline period will be 6 months prior to the treatment index.

Population

The study cohorts will be identified during the selection window from 01 January 2018 to 30 November 2022. Based on the treatment (apixaban or warfarin) received during the VTE hospitalization, patients will be classified into apixaban and warfarin cohorts. Patients will be required to have medical and pharmacy activity during the 6 month pre-hospitalization period and 1-month post-hospitalization period i.e. post-discharge. Following discharge, patients will be indexed to either apixaban or warfarin based on the first observed outpatient pharmacy claim for the respective therapy, and will have a 6-month baseline period prior to the treatment index date and a variable follow-up period after the treatment index date. Treatment patterns and clinical outcomes will be evaluated during the variable follow-up period.

Variables

Exposures and explanatory variables on the treatment index date and 6-months prior to the treatment index period (which includes the hospitalization)

- Demographic characteristics
- Clinical characteristics

Characteristics of hospitalization

- Hospital characteristics

Outcomes

- Apixaban and warfarin treatment rates during hospitalization

- Post-discharge continuity (i.e. persistence of hospitalization treatment/treatment discontinuation or switch)
- Post-discharge treatment patterns among those who continue the same treatment provided during hospitalization (persistent days, discontinuation, switching)
- Post treatment-index recurrent VTE and bleeding hospitalizations

Data sources

IQVIA's CDM database linked with Dx and LRx will be utilized for this analysis. IQVIA's CDM is comprised of hospital-based data which are sourced from hospital CDM files. CDM covers more than 450 hospitals per month and approximately 8 million inpatient visits and 105 million outpatient visits per year. Dx database includes outpatient medical claims which will be necessary for describing baseline clinical characteristics. Dx database captures over one billion pre-adjudicated claims and three billion records obtained annually from approximately 800,000 office-based physicians and specialists. LRx database captures information on dispensed prescriptions sourced from retail, mail, long-term care, and specialty pharmacies. IQVIA has industry-leading coverage in the following channels: 92% coverage of the retail channel, 72% coverage of standard mail service, and 76% of long-term care facilities. LRx will be necessary for describing baseline treatment history and reporting post-index treatment patterns.

Study size

All eligible patients will be included in the study.

Data analysis

Descriptive analysis will be conducted for all relevant study measures for the two cohorts of interest. No comparisons will be conducted in this analysis. Four multivariable regression models or Cox proportional hazards model will be conducted to evaluate factors associated with outcomes of interest. All analyses will be based on observed, not projected data. Analyses will be conducted using Statistical Analysis System® (SAS) Release 9.4 (SAS Institute Inc., Cary, NC), and the results will be reported in Excel tables.

Milestones (tentative)

| | |
|-------------------------|--------------------|
| Protocol approval: | 17 February, 2023 |
| Start of data analysis: | 27 February , 2023 |
| Final results: | 05 May, 2023 |
| Final study report: | 09 June, 2023 |

5. AMENDMENTS AND UPDATES

None

| Amendment number | Date | Protocol section(s) changed | Summary of amendment(s) | Reason |
|-------------------------|-------------|------------------------------------|--------------------------------|---------------|
| 1 | | | | |
| 2 | | | | |

6. MILESTONES

| Milestone | Planned date |
|---------------------|---------------------|
| Protocol approval | 17 February, 2023 |
| Start of analysis | 27 February, 2023 |
| Analysis completion | 05 May, 2023 |
| Final study report | 09 June, 2023 |

7. RATIONALE AND BACKGROUND

Venous thromboembolism (VTE), comprising deep vein thrombosis (DVT) and pulmonary embolism (PE), is a major health concern associated with significant mortality and morbidity. It is the third most common cause of vascular disease-related death and poses a substantial economic burden to the healthcare system. In the United States (US), approximately 1 million people develop symptomatic VTE each year.^{1,2} There are >330,000 hospital admissions for VTE every year in the United States (US).³ Historical data suggests that the rate of hospitalizations for VTE increased from 7.0 to 8.4 per 1,000 discharges in the US.⁴

Management of VTE during an acute hospital encounter involves rapid anticoagulation. Current guidelines recommend continuing anticoagulation therapy post-discharge with vitamin K antagonists such as warfarin, or one of the newer direct oral anticoagulants (DOAC) which do not require PAC bridging therapy.⁵ Over the past decade, the use of DOACs, particularly apixaban to treat VTE has increased dramatically.⁶

There are some gaps in RWE regarding OAC use among patients hospitalized with VTE. First, there is need for RWE regarding the proportion of patients treated with particular OAC during the VTE hospitalization. Second, there needs to be a better understanding of the OAC-related treatment patterns post-discharge following VTE hospitalizations. There is evidence that a large proportion of patients treated in inpatient and observational hospital settings do not fill an anticoagulant prescription post-discharge⁷. Research shows that the choice of treatment regimen and/or setting could influence the likelihood of post-discharge continuation of OAC medication.⁷ This study will investigate the initial treatment patterns during VTE hospitalization and further investigate the treatment patterns and factors associated with poor outcomes among these patients.

The study team, comprised of members from Pfizer and Bristol Myers Squibb (hereon referred to as the 'Alliance'), is collaborating with IQVIA in conducting a study to assess treatment patterns and health outcomes post hospital discharge for VTE.

090177e19cc79c7f\Approved\Approved On: 03-Mar-2023 00:48 (GMT)

8. RESEARCH QUESTION AND OBJECTIVES

The purpose of this study is to evaluate the post-discharge treatment patterns including persistence and outcomes such as recurrent VTE and bleeding among hospitalized adults with VTE treated with apixaban or warfarin.

The study objectives are to:

1. Describe the proportion of patients with VTE treated with apixaban or warfarin in the hospital
2. Understand the post-discharge treatment patterns (including persistence, switch, and discontinuation) among patients who started on apixaban or warfarin in the hospital

The secondary objective is to:

3. Assess recurrent VTE, major bleeding, and clinically relevant non-major (CRNM) bleeding among patients who continue on apixaban or warfarin in the outpatient setting while persistent on index therapy

[figure not shown]
9. RESEARCH METHODS

A retrospective database analysis will be conducted among patients hospitalized with a primary diagnosis of VTE. This study will utilize linked data from IQVIA’s hospital charge data master (CDM), professional fee claims (Dx) and longitudinal prescription claims (LRx) using data from 01 July 2017 through 31 December 2022 or the latest available data at the time of extraction (i.e., the study period), including a 6-month pre-hospitalization period (to confirm study eligibility) and minimum 1-month post-hospitalization period (to identify post-discharge treatment). Following discharge, patients will be indexed to the apixaban or warfarin cohort, based on the first observed outpatient pharmacy claim for the respective therapy. A 6-month pre-treatment index period (baseline) will be applied to capture demographic and clinical characteristics, and a variable follow-up period will be used to capture post-treatment index patterns and clinical outcomes.

9.1. Study period and study design

The analysis will be conducted using data from 01 July 2017 through 31 December 2022 or the latest available data at the time of extraction (i.e., the *study period*). Figure 1 illustrates the study schematic for this project. The study cohorts will be identified during a selection window from 01 January 2018 to 30 November 2022. The date of the first treatment with apixaban or warfarin during the hospitalization will be flagged. Based on this treatment during the VTE hospitalization, patients will be classified into the apixaban and warfarin cohorts. Patients will be required to have medical and pharmacy activity during the 6 months prior to the admit date of the hospitalization (pre hospitalization period) and 1-month (minimum) from the discharge date of the hospitalization (post hospitalization period). The date of the first outpatient prescription for apixaban or warfarin on or within 30 days after discharge date from the hospitalization will be termed as ‘treatment index date’.

Figure 1. Study Period

*Latest available data at the time of extraction will be utilized for this study

9.1.1. Inclusion criteria

Patients must meet all of the following inclusion criteria to be eligible for inclusion in the study:

1. Patients with an inpatient hospitalization with admit date and discharge date between 01 January 2018 and 30 November 2022 (selection window) in CDM with a primary diagnosis of VTE

Note: The admit date of the first hospitalization with primary diagnosis of VTE during the selection window will be flagged. Only patients with overnight stays with discharge date after the admit date (to confirm inpatient stay with overnight admission) will be included in the study.

Note: Number of patients who died during hospitalization (identified from discharge disposition measure) will be reported and these patients will be excluded from the study.

2. With evidence of receiving apixaban or warfarin during the hospitalization

Note: The date of the record with first apixaban or warfarin administration during the hospitalization will be flagged as the start of apixaban or warfarin treatment. Patients will be assigned to the apixaban or warfarin cohort based on this treatment received during hospitalization.

3. With linkage to LRx between 01 July 2017 and 31 December 2022 (i.e. study period)
4. With linkage to Dx during the study period
5. With activity in the 6 months prior to the admit date of hospitalization, defined as ≥ 1 claim in Dx and ≥ 1 prescription claim in LRx (pre hospitalization period)
6. With activity in the 1-month after the discharge date of hospitalization, defined as ≥ 1 claim in Dx and ≥ 1 prescription claim in LRx (variable post hospitalization period)
Note: Patients will have a minimum 1-month post discharge period (to capture outpatient treatment)
7. With age ≥ 18 years on apixaban or warfarin administration date during index hospitalization

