9.2.2. Outcome measures

The following outcome measures are assessed post-discharge, and will be measured during the variable post-index period starting on the treatment index date for the apixaban and warfarin cohorts.

Treatment patterns

- Persistent days (mean, SD, median, IQR, min, max) will be reported for patients until they discontinue, switch or end of follow-up based on definitions below
- Patients discontinuing outpatient treatment of apixaban or warfarin, respectively (NDC codes from LRx; n, %)

Note: Discontinuation will be defined as the occurrence of a ≥ 30 day gap from the run-out of days' supply of the treatment (post-discharge) index prescription (i.e. apixaban or warfarin) to the date of the next claim for the respective therapy or with no other claims for the respective therapy. The date of the discontinuation will be defined as the last day of the days' supply of the last filled prescription.

- Time (in days) from treatment index date to discontinuation date (mean, SD, median, IQR, min, max)

Note: Kaplan-Meier (KM) curves will be generated to measure median time (and 95 % CI) to discontinuation.

- Patients switching to an OAC other than apixaban or warfarin, respectively (switched) (NDC codes from LRx; n, %)

Note: Patients will be considered to have switched if they filled a prescription for OAC other than apixaban or warfarin, respectively (identified through NDC codes in LRx) or for PAC within 30 days before or after the run out date of index treatment. The date of the switch will be defined as date of the prescription of such a therapy (OAC or PAC).

- Time (in days) from treatment index date to switch date, defined as the date of the first claim for the new OAC or PAC (mean, SD, median, IQR, min, max)

Note: KM curves will be generated to measure median time (and 95 % CI) to switching

Clinical Outcomes

The following clinical outcomes will be assessed during the time patients are persistent with their respective index apixaban or warfarin treatment (treatment index):

- Patients with ≥ 1 hospitalization for recurrent VTE (ICD-10 codes in CDM; n, %)
- Incidence rate (IR) of recurrent VTE (per 100 patient years)
 - The date of the first observed event will be flagged. The numerator for IR will be the number of patients with the event of interest and denominator will be the ‘at risk’ period i.e. the time to first event. The 95% confidence intervals (CI) will also be reported.

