Note: Recurrent VTE will be defined as inpatient hospitalization with a primary diagnosis of VTE occurring 7 or more days after the first hospitalization discharge date.

- Time (days) from first hospitalization discharge date to first recurrent VTE hospitalization (mean, SD, median, IQR, min, max)
- Time (days) from treatment index date to first recurrent VTE hospitalization (mean, SD, median, IQR, min, max)
- Patients with ≥ 1 hospitalization for major bleeding (ICD-10 codes in CDM; n, %)
- IR of major bleeding (per 100 patient years)

Note: Major bleeding will be defined as inpatient hospitalization with primary diagnosis of gastro-intestinal bleeding, intracranial hemorrhage (ICH) or other major bleeding

- Time (days) from first hospitalization discharge date to first major bleeding episode (mean, SD, median, IQR, min, max)
- Time (days) from treatment index date to first major bleeding episode (mean, SD, median, IQR, min, max)
- Patients with ≥ 1 CRNM bleeding event (n, %)
- IR of CRNM bleeding (per 100 patient years)

Note: CRNM bleeding will be defined as inpatient hospitalization with a secondary diagnosis code for bleeding (without a major bleeding code in the primary position) or an outpatient encounter with a diagnosis code in any position for CRNM GI bleeding or other non-critical types of bleeding. Specifically, it is defined as:

(1) An inpatient admission with a secondary diagnosis for “noncritical site” bleeding such as GI bleeding or other selected noncritical types/sites of bleeding (excluded if major bleeding occurred during the same hospitalization), OR

(2) An outpatient encounter with a diagnosis code for GI bleeding and other selected noncritical types/sites of bleeding.

Any CRNM bleeding events (as described above) that follow a major bleeding event (described above) will not be included in the analysis of CRNM bleeding

- Time (days) from first hospitalization discharge date to first CRNM bleeding episode (mean, SD, median, IQR, min, max)
- Time (days) from treatment index date to first CRNM bleeding episode (mean, SD, median, IQR, min, max)

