IQVIA's Dx database captures over one billion pre-adjudicated claims and three billion records obtained annually from approximately 800,000 office-based physicians and specialists. Dx database is updated on a weekly basis with approximately a 30-60 day lag for data completeness. Key information includes International Classification of Diseases, ninth revision, clinical modification (ICD-9-CM) and International Classification of Diseases, tenth revision, clinical modification (ICD-10-CM) diagnoses, CPT/procedure/Healthcare Common Procedure Coding System (HCPCS) for medical conditions and procedures, date of service, location of care, (pre-adjudicated) charged amount for service, payer types (commercial, Medicaid, Medicare, cash payment), patient age and sex. Note that inpatient data is limited.

Longitudinal Prescription Claims (LRx)

IQVIA LRx database captures information on dispensed prescriptions sourced from retail, mail, long-term care, and specialty pharmacies. These suppliers have direct, long-standing relationships with IQVIA, with many providing data on a daily basis, and all suppliers support weekly data feeds with an ability to provide insight within ten days of the end of each week. This enables IQVIA to ensure that the LRx database has good longitudinal, representative, and current data from consistent and stable suppliers. IQVIA has industry-leading coverage in the following channels: 92% coverage of the retail channel, 72% coverage of standard mail service, and 76% of long-term care facilities. IQVIA receives specialty data directly from the pharmacy resulting in near census data coverage, contributing to greater precision for longitudinal analysis. Additionally, diagnosis is included directly on the majority of specialty pharmacy transactions from the specialty pharmacy providers. An important strength of the LRx database for this analysis is the longitudinal capture of adjudicated and cash prescriptions for all age categories, regardless of insurance type.

Linkage Methodology

A proposed dataset will be constructed utilizing patient data from LRx, Dx and CDM, with the appropriate dataset being selected based upon proportion of linked patients. This process which is compliant with The Health Insurance Portability and Accountability Act of 1996 (HIPAA) is described below:

- IQVIA has developed a patented and proprietary encryption algorithm that utilizes actual patient-level information to create a unique Patient identifier (ID)⁸

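### The post-discharge Dx claim required by inclusion criterion 6 can fall after outcome follow-up has started, so an outpatient bleed recorded in Dx can qualify its own patient; the effect is probably small and cheap to check

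*Combined protocol and SAP*

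**What the plan says.** - **Eligibility.** Section 9.1.1, criterion 6, reads "With activity in the 1-month after the discharge date of hospitalization, defined as ≥ 1 claim in Dx", and it also asks for at least one LRx claim. The Abstract has the post-hospitalization period "starting a day after discharge date of hospitalization". The note under criterion 6 gives the purpose: "Patients will have a minimum 1-month post discharge period (to capture outpatient treatment".
- **Time zero.** Section 9.1 defines the treatment index date as "The date of the first outpatient prescription for apixaban or warfarin on or within 30 days after discharge date". Section 9.2.2 says that outcomes "will be measured during the variable post-index period starting on the treatment index date for the apixaban and warfarin cohorts".
- **CRNM bleeding.** One of the two routes to an event in section 9.2.2 is "An outpatient encounter with a diagnosis code for GI bleeding" or for another selected noncritical bleed. No database is named for it. Recurrent VTE and major bleeding are hospitalizations taken from CDM.
- **Dx.** The Abstract describes it as holding outpatient medical claims. Section 9.3 says that it comes from office-based physicians and adds: "Note that inpatient data is limited".
- **Related rules.** Section 9.2, item 1c, excludes patients with an event between discharge and the treatment index date. Item 1d ends follow-up no later than the last medical claim or last prescription in Dx/Rx. Section 9.8 says that activity proxies stand in for continuous enrolment and that mortality is not captured.

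**The concern.** A cohort should be fixed by what is known at or before time zero. Here a patient who fills promptly has most of the criterion 6 month still ahead when follow-up begins, so events in that time can help decide who is in the cohort.

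For CRNM bleeding the link is direct: an outpatient bleed seen in Dx is both an outcome and a qualifying claim. Patients with such bleeds are kept, while some bleed-free patients are dropped, and the rate rises. A patient who dies before any Dx claim is removed along with any event, and without mortality data that loss cannot be measured afterwards.

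At stake are the objective 3 rates. The section 9.6 Cox models of clinical events, with treatment as the main effect, are also affected if the chance of having a Dx claim differs by drug. Item 1c deals only with events before the treatment index date, section 9.8 does not mention selection on later activity, and no sensitivity analysis is planned.

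**Working it through.** The plan gives no figure to reproduce: no event rate, no Dx claim probability, and only feasibility counts in section 9.4.

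**1. Overlap.** The criterion 6 window runs for one month from the day after discharge. Follow-up starts on day 0 to 30. For any fill before the end of the window, the remaining days belong to both. The qualifying claim can also fall before the fill, so the overlap is possible rather than certain for a given patient.

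**2. First-month factor.** Let r be the true first-month risk, p the chance of at least one Dx claim in the month without the event, and q that chance with the event. All three are assumptions. Then

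observed / true = q / (r·q + (1 − r)·p), which is about q/p for small r.

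A bleed recorded in Dx has q = 1, so the factor is about 1/p:

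| Assumed p | 1/p | Exact, r = 0.02 |
|---|---|---|
| 0.95 | 1.05 | 1.05 |
| 0.90 | 1.11 | 1.11 |
| 0.75 | 1.33 | 1.32 |
| 0.60 | 1.67 | 1.64 |

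**3. Dilution in the reported rate.** Objective 3 uses one incidence rate over all persistent time. Assume a constant hazard, 180 days at risk, and fills on days 0, 1, 2, 5, 10 and 20 with shares 0.50, 0.20, 0.10, 0.10, 0.06 and 0.04. The mean fill day is 0.2 + 0.2 + 0.5 + 0.6 + 0.8 = 2.3, so the share of follow-up inside the window is w = (30 − 2.3)/180 = 0.154. The factor is about 1 + w(1/p − 1):

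| Assumed p | 1 + 0.154(1/p − 1) | Simulation |
|---|---|---|
| 0.95 | 1.008 | 1.008–1.009 |
| 0.90 | 1.017 | 1.017–1.018 |
| 0.75 | 1.051 | 1.050–1.055 |
| 0.60 | 1.103 | 1.106–1.109 |

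The simulation used 2,000,000 patients per scenario, with assumed rates of 20 outpatient CRNM bleeds and 4 hospitalized events per 100 patient-years.

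**4. Between cohorts.** Take p = 0.85 for apixaban and 0.95 for warfarin (assumed). The first-month ratio shifts by (1/0.85)/(1/0.95) = 1.12. Over 180 days, p = 0.85 gives 1 + 0.154 × 0.176 = 1.027, and 1.027/1.008 is about 1.02.

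**5. Hospitalized events.** A CDM record does not meet criterion 6, so q need not be 1. The same simulation, for p from 0.60 to 0.95 with a 6-day stay that yields no Dx claim, gives these observed/true ratios:

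| Office-visit rate after event | Fatal share | First month | 180 days |
|---|---|---|---|
| Unchanged | 0% | 0.88–0.97 | 0.982–0.995 |
| Unchanged | 20% | 0.83–0.92 | 0.975–0.987 |
| Tripled | 0% | 1.02–1.16 | 1.003–1.019 |
| Tripled | 20% | 0.97–1.04 | 0.995–1.011 |

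The sign depends on assumptions that the documents do not settle. Only an event fatal before any Dx claim has a fixed answer: q = 0, and it is lost.

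**The case against.** **Open claims data need some proof of visibility.** Patients without a post-discharge Dx claim include some who made no visit and some whose providers do not report to Dx. Outpatient bleeds in the second group cannot be seen there, and keeping those patients would push the CRNM rate down. This stands, and it argues against simply deleting the Dx half. It does not justify taking visibility from after time zero: criteria 4 and 5 already require Dx linkage and pre-admission Dx activity, and the month's stated purpose is served by LRx.

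**Not every bleed self-qualifies.** CDM also covers outpatient and emergency encounters, and CRNM bleeding can be an inpatient secondary diagnosis. Neither meets criterion 6 through CDM. A reader might infer that all patients with bleeds enter with certainty. That holds only for bleeds recorded in Dx, so 1/p is an upper bound.

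**Early hospitalized events need not drop out.** A reader might infer that major bleeding and recurrent VTE are understated. Dx inpatient data are limited but not said to be absent, a visit before the event also qualifies, recurrent VTE counts only from day 7 after discharge, and follow-up visits may raise q above p. The downward direction is not supported.

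**Criterion 6 is not the only cause.** Item 1d can end follow-up before a CDM event whatever criterion 6 says. The one-month minimum in the note, if read as required observed time, would also remove early deaths.

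**The plan leaves room to act.** Section 9.1.2 foresees an attrition table at which criteria may be modified, but it does not promise a row for this step by cohort.

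**Conclusion.** The point holds in a limited form. Criterion 6 selects partly on activity after time zero, and a CRNM bleed recorded in Dx can qualify its own patient. The result is upward pressure on the CRNM rate: at most about 1.05 to 1.33 in the first month for assumed p of 0.95 to 0.75, and about 1.01 to 1.05 in the reported rate over an assumed 180 days at constant hazard. Front-loaded bleeding or shorter persistence would dilute it less; the documents give neither.

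The first-month factors should not be read as the bias in a planned result, because no first-month rate is planned. The between-cohort shift of about 1.02 is conditional: the documents give no Dx visit frequency by drug. Deaths before any Dx claim are lost, in unknown number. For non-fatal major bleeding and recurrent VTE no direction can be claimed. This is a worthwhile, inexpensive improvement and does not undermine the study.

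**What to change.** 1. In the section 9.1.2 attrition table, add a row that gives, by cohort, the number removed by the Dx half of criterion 6 alone. This supplies the missing information on p and on whether it differs by drug.
2. Add a sensitivity analysis that repeats the objective 3 rates and the section 9.6 Cox models without the post-discharge Dx claim, with Dx visibility resting on criterion 5.
3. In that rerun, do not let the last-medical-claim rule in section 9.2, item 1d, end follow-up before a CDM event. Apply the changed rule to all patients, with and without events, so that events and person-time are treated alike.
4. Name the database or databases for outpatient CRNM bleeds in section 9.2.2, and add a sentence on this selection to section 9.8.

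The cost is one attrition row, one extra run and a few lines of text. The downside is that some patients with weaker Dx visibility enter the sensitivity set, which may understate outpatient bleeds there. The main and sensitivity results should therefore be read side by side.
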